### **2. Completion of the questionnaires**

Primary care physicians will complete the Clinical Utility and Satisfaction Questionnaire (Annex I) twice during the study, the first time at 2 months and the second time at 4 months from the start of the study.

## **Procedures to be performed by the specialist physician**

### **1. Consultation**

The Principal Investigator will see patients while maintaining their standard clinical routine. In the Data Collection Document (DCD), they will note the appropriateness of the patient referral. If they deem the referral to dermatology inappropriate, this will also be recorded. The initial diagnosis provided by the primary care physician, as well as their own diagnosis, will be documented. If relevant, the pathology diagnosis will also be included.

### **2. Completion of questionnaires**

Dermatologists will complete the Clinical Utility and Satisfaction Questionnaire (Annex I) twice during the study, the first time at 2 months and the second time at 4 months from the start of the study.

---

## 6. Ethical considerations

### **Ethical considerations, regarding information to subjects and informed consent**

The study will be conducted in accordance with international Good Clinical Practice guidelines, the Declaration of Helsinki in its latest amendment, and applicable international and national rules and regulations. It will not commence until it has received approval from the Research Ethics Committee of the Puerta de Hierro Majadahonda University Hospital. Any modification to this protocol will be reviewed and approved by the Principal Investigator and must be evaluated by the Ethics Committee for its approval before enrolling subjects in a modified protocol.

The study will be conducted in accordance with European Regulation 2016/679 of 27 April, on the protection of natural persons with regard to the processing of personal data and on the free movement of such data, and Organic Law 3/2018 of 5 December, on the Protection of Personal Data and Guarantee of Digital Rights, with regard to data processing. No data that allows for the personal identification of subjects will be included, and all information will be managed in a coded manner.

Patients will be informed orally and in writing about all aspects of the study, adapted to their level of understanding. Patients will be given a copy of the informed consent form and information sheet. The investigator must allow patients sufficient time to ask questions about the details of the study.

The preparation of the informed consent form is the responsibility of the Principal Investigator. This form must include all elements required by the International Conference on Harmonisation (ICH), current regulatory guidelines, and comply with Good Clinical Practice (GCP) guidelines and the ethical principles derived from the Declaration of Helsinki.

The investigator, or a person designated by the Principal Investigator, will keep the original signed informed consent form in a secure, restricted-access area, under the custody of the Principal Investigator. This form will never leave the facility, and a copy of the original signed form will be given to the patient.

### **Considerations on the treatment of biological samples**

Biological samples will not be collected in this study.

### **Data confidentiality**

Regarding the confidentiality of the study data, the provisions of Organic Law 3/2018, of December 5, on the Protection of Personal Data and Guarantee of Digital Rights and Regulation (EU) General Data Protection Regulation 2016/679 will be followed.

---

## **Interference with the practitioner's prescribing habits**

The clinical management of patients will be adapted to the treatment standards of the Dermatology Service of the Puerta de Hierro Majadahonda University Hospital, without the performance of this study influencing such process.

## **7. Plan for disseminating the results**

Following the completion of the study, the results of the clinical utility and satisfaction surveys, conducted according to the model in Annex I, may be presented at conferences and scientific meetings with prior authorization from both parties. Press releases and communications may also be issued to communicate the study results. All publications and communications must be accepted and approved by Novartis and the Puerta de Hierro Majadahonda University Hospital.

## **8. Protocol modifications**

Any modification to the study protocol will always take the form of a written amendment or addendum. Formalization will require the approval of all individuals responsible for the study. In the case of significant modifications, express approval from the Clinical Research Ethics Committee will be requested.

## **9. Practical considerations**

### **Start, progress and end reports**

The ethics committee will be notified of the start of the study. Annual progress reports will be submitted subsequently.

After the study's conclusions are reached, a final report will be prepared and submitted to the ethics committee.

## 11. Annexes

### Annex I - Clinical Utility and Satisfaction Questionnaire

Based on their experience, without needing to consult the Medical History:

1. Average weekly number of patients with skin conditions you have seen in your practice during the last two months (approximate).
2. Name the conditions for which Legit.Health has been most useful in your daily clinical practice.
3. In your opinion, indicate the impact of Legit.Health from 0 to 10 (where 0 is “no impact” and 10 is “great impact”) on the accuracy of your diagnostic decisions for each of the following diseases:
  - a. Urticaria
  - b. Psoriasis
  - c. Hidradenitis Suppurativa
  - d. Melanoma
  - e. Atopic Dermatitis
  - f. Other (add any other diseases where the tool has had an impact at this point and rate the impact from 0 to 10)
4. In your opinion, please indicate the impact of Legit.Health from 0 to 10 (where 0 is “no impact” and 10 is “great impact”) in relation to reducing the time to issue your diagnostic decision for each of the following diseases:
  - a. Urticaria
  - b. Psoriasis
  - c. Hidradenitis Suppurativa
  - d. Melanoma
  - e. Atopic Dermatitis
  - f. Other (add any other conditions where the tool has had an impact at this point)
5. In your opinion, please indicate the impact of Legit.Health from 0 to 10 (where 0 is “no impact” and 10 is “great impact”) on your therapeutic decision-making, thanks to the included management recommendations, for each of the following diseases:
  - a. Urticaria
  - b. Psoriasis
  - c. Hidradenitis Suppurativa

- 
- d. Melanoma
  - e. Atopic Dermatitis
  - f. Other (add any other conditions where the tool has had an impact at this point)
6. In your opinion, please indicate the impact of Legit.Health from 0 to 10 (where 0 is “no impact” and 10 is “great impact”) on monitoring the evolution of skin lesions for each of the following diseases:
- a. Urticaria
  - b. Psoriasis
  - c. Hidradenitis Suppurativa
  - d. Melanoma
  - e. Atopic Dermatitis
  - f. Other (add any other conditions where the tool has had an impact at this point)
7. In your opinion, please indicate the impact of Legit.Health from 0 to 10 (where 0 is “no impact” and 10 is “high impact”) on the efficiency of interconsultations/referrals to the dermatology service (in cases where referral applies) for each of the following diseases:
- a. Urticaria
  - b. Psoriasis
  - c. Hidradenitis Suppurativa
  - d. Melanoma
  - e. Atopic Dermatitis
  - f. Other (add any other conditions where the tool has had an impact at this point)
8. Please indicate your overall level of satisfaction with the use of Legit.Health from 0 to 10 (where 0 is “not at all satisfied” and 10 is “very satisfied”).

Would you recommend Legit.Health to other primary care colleagues?

In your opinion, please indicate your patients' level of satisfaction with using Legit.Health from 0 to 10 (where 0 is "not at all satisfied" and 10 is "very satisfied").

Would you recommend using Legit.Health to your patients?

Are there any additional features you would consider relevant to include in this tool? Open field

---

Are there any features already included in the tool that you consider irrelevant or that do not add value to your clinical practice? Open field

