## 2. Theoretical framework. Problem statement.

### Background and rationale

Skin-related diseases are a frequent reason for consultation in primary care (PC); some studies estimate this at approximately 5% of all consultations, mainly among the working population.

This represents a considerable consumption of resources and makes an efficient approach to these conditions a key step in optimizing the functioning of primary care.

Numerous studies show discrepancies in opinion between primary care physicians and dermatologists, with agreement rates in their diagnoses ranging from 57% to 65.52% depending on the study. In general, primary care physicians do not demonstrate adequate knowledge about skin diseases, their diagnosis, and their treatments.

This human limitation when evaluating skin diseases is also reflected in the effort and time required to estimate the degree of involvement in a patient or the stage of the pathology. So much so, that it ends up being a very unrewarding task and can lead to poor adherence to the protocol and inappropriate referrals. Time consumption is especially concerning given that the number of medical professionals, particularly in dermatology, is insufficient to meet the existing demand. Access to a dermatology specialist for the general population is complicated due to the low number (3 dermatologists per 100,000 inhabitants), a situation that is even more difficult in small population centers. Because of this, screening for dermatological lesions must be carried out by primary care physicians, whose diagnostic capacity is even lower and which may increase the risk of misdiagnosis.

In this regard, the literature shows a discrepancy of between 55% and 65% between primary care physicians and specialists, and studies confirm several expected characteristics: common dermatological diseases are often not recognized or are misdiagnosed by non-dermatologists due to the particular profiles of common diagnoses in this field (drug-induced rashes, fungal infections).

In addition to these inherent limitations, when the preliminary examination is performed by the patient, the possibility of bias arises. This is especially true

when the patient knows that the treatment they receive will be determined by the information they provide. Furthermore, the medical team lacks the means to verify the accuracy of the values reported by the patient, preventing external verification.

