**Variables**

The main variable aims to determine the clinical utility of the platform developed by AI LABS GROUP SL in the management of patients with skin pathology by primary care physicians and dermatologists of the Puerta de Hierro Majadahonda University Hospital involved in the project.

For this purpose, clinicians will complete the **Clinical Utility and Satisfaction Questionnaire (Annex I)**.

In addition, the following secondary variables will be collected::

- Patient demographics:
  - Sex
  - Age
- Teleconsultation data:
  - Response time
  - Response label (follow-up in primary care, shared follow-up, dermatology follow-up, insufficient or inadequate information)
- Data from the in-person consultation:

- Duration of an in-person dermatology appointment to respond to an online primary care consultation.
- Waiting time until being seen in a specialized dermatology clinic.
- Diagnosis
  - Diagnostic correlation between primary care and dermatology.
  - Number of patients referred by pathology.
  - Diagnostic correlation between primary care, dermatology, and dermatopathology (if applicable).
  - Time elapsed between the day of the primary care visit and the day of the histopathological diagnosis (if applicable).
- Primary care physician satisfaction using the Clinical Utility and Satisfaction Questionnaire (Appendix I).
- Dermatologists satisfaction using the Clinical Utility and Satisfaction Questionnaire (Appendix I).

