### **Expected sample size**

This study will recruit 100 patients. This study is designed as a proof-of-concept pilot study in which the sample size has been estimated based on the number of primary care physicians who treat patients diagnosed with skin diseases who can be seen in the primary care services of the following centers:

1. Majadahonda Health Center
2. Pozuelo Health Center

During the study recruitment period, all patients diagnosed with skin diseases who meet the selection criteria will be included.

To ensure that all primary care physicians participating in the study have sufficiently interacted with the tool, a minimum of 50 patients per primary care center is required.

The data collected from these patients during the study period will be analyzed, and based on the results, an assessment will be made as to whether it is necessary to expand the sample size to include more patients.

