## **Procedures to be performed by the primary care physician**

### **1. Consultation**

Primary care physicians will need to take photographs showing the areas affected by the condition. These photographs will be taken with their own smartphone or using a mobile dermatoscope if its use is clinically relevant. Primary care physicians will upload the photographs to the Legit.Health platform.

Primary care physicians will assess the patient's condition through direct observation and guided by the results from the platform. They will enter the diagnosis into the Legit.Health platform by selecting the condition if it is among the first 5 or by using a drop-down menu that displays a wide range of conditions.

In addition to the most likely diagnoses, physicians will have access to referral criteria, the clinical referral questionnaire, and basic treatment advice. When they deem it necessary, they will refer the patient in their Selene system, as they normally would; not through Legit.Health.

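### Annex I items 3-7 rate impact by disease without limiting it to patients assessed with Legit.Health or counting them, so the main variable cannot separate benefit per use from frequency of use

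*Combined protocol and SAP*

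**What the plan says.** Section 4, Variables, states the purpose of the main variable: "The main variable aims to determine the clinical utility of the platform developed by AI LABS GROUP SL in the management of patients". It names the Annex I questionnaire as the means of measuring it and gives no scoring rule. Primary care physicians and dermatologists both complete the form, at 2 and 4 months.

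Annex I is answered from memory: "Based on their experience, without needing to consult the Medical History". Its parts bear on this point as follows:

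- Item 1 is the only question about volume. It asks for "Average weekly number of patients with skin conditions you have seen in your practice during the last two months (approximate".
- Items 3-7 each ask for a 0-10 impact rating for five named diseases plus a free *other* line. Item 3, for example, asks about impact "on the accuracy of your diagnostic decisions for each of the following diseases". Items 4-7 do the same for time to diagnosis, therapy, monitoring and referral.
- The only case restriction in items 3-7 is in item 7, "in cases where referral applies". It concerns referral, not use of the tool.
- None of items 3-7 states a time window or offers an answer for a disease in which the tool was not used.

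On exposure, Expected sample size says "This study will recruit 100 patients" and requires at least 50 patients per centre, so that participating physicians have had enough contact with the tool. It sets no minimum per physician or per disease.

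**The concern.** A rating of impact on one's decisions in psoriasis has two natural readings. One is how much the tool helped in the psoriasis patients in whom it was used. The other is how much it changed the respondent's handling of psoriasis overall. The two agree only if the tool was used in nearly all such patients. Items 3-7 do not say which is meant, and no answer on the form lets an analyst work it out afterwards.

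This affects the interpretation of the main variable. If respondents differ in their reading, average ratings are not comparable between physicians, between diseases, or between the 2-month and 4-month forms. A physician who never used the tool in a named disease has no way to say so. A zero may then mean no benefit or no exposure.

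**Working it through.** **The plan's own figure.** Two centres × a minimum of 50 patients = 100, which reproduces the stated sample size. No alpha, power or effect size is given, so no sample-size formula applies.

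**Exposure that follows from the documents.** Recruitment lasts 4 months, or 4 × 52/12 = 17.33 weeks.

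- Both centres: 100 / 17.33 = 5.77, about 5.8 tool patients per week.
- Each centre: 50 / 17.33 = 2.88, about 2.9 per week.

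**Exposure per disease.** The inclusion criteria list 16 conditions. Assuming an even mix, which the documents do not state:

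- Whole study: 100 / 16 = 6.25 patients per condition.
- Each centre: 50 / 16 = 3.1.
- Each centre at the 2-month form, assuming steady recruitment: 25 / 16 = 1.6.

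**Exposure per physician.** The number of physicians is not stated, so a range is assumed. With k physicians per centre, each has m = 50/k tool patients over 4 months, and half that by month 2. Under the even mix, the chance that a physician has had no tool case of a given named disease is (15/16)^m.

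| Physicians per centre (assumed) | Tool patients each, 4 months | No case by month 2 | No case by month 4 |
|---|---|---|---|
| 3 | 16.7 | 58% | 34% |
| 5 | 10 | 72% | 52% |
| 10 | 5 | 85% | 72% |
| 15 | 3.3 | 90% | 81% |

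These percentages illustrate why a *not used* answer is needed. They are not estimates for this study.

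**Why the ratings cannot be separated.** Let u be the benefit per use on the 0-10 scale and c the share of that disease's patients assessed with the tool. A per-use respondent reports u. A respondent rating the whole disease reports, in the simplest model, u × c. Then 8 × 0.25 = 2 and 2 × 1.00 = 2. A tool that helps greatly in a quarter of patients and one that helps little in all of them get the same score. The form collects neither c nor the number of uses.

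**Whether item 1 supplies it.** It does not. Item 1 covers every skin condition, including those outside the 16 listed, and also patients who did not consent or were seen without the tool. It is not split by disease, whereas the ratings are.

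**Whether another section supplies it.** The platform will hold the cases: under Procedures to be performed by the primary care physician, Consultation, "They will enter the diagnosis into the Legit.Health platform by selecting the condition if it is among the first 5". No section uses those records as a count of use, and Patient identification says that patients' data will not be analysed or processed.

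**The case against.** The strongest reply is the inclusion rule in Expected sample size: every patient who meets the selection criteria during recruitment is to be enrolled. All five named diseases are on the inclusion list. If that rule is followed, the tool is used in nearly every eligible adult with those diseases, c is close to 1 and the two readings largely converge. This stands in part. Non-consent, the exclusion criteria and the target of 100 leave a gap that the documents do not allow anyone to size, and the form would not show it.

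Second, parts of the form point towards actual use. The *other* lines ask for diseases in which the tool made a difference, item 5 refers to its management recommendations, and item 8 rates satisfaction with using it. Many physicians may well answer per use. So the defect is that the form cannot separate the readings, not that it is known to mix them. It is also confined to items 3-7.

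Third, practice-wide impact is itself a legitimate target, since item 2 and the research questions speak of everyday practice. That is fair, but the form should then say which target it means.

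A reader might go further and infer that item 1 overstates tool use many times over. The route is the background statement that "some studies estimate this at approximately 5% of all consultations" combined with an assumed 100-200 weekly consultations per physician and 5-15 physicians per centre. That gives 5-10 skin patients per physician per week against 0.19-0.58 tool patients, a 9- to 52-fold excess, and suggests that a decisive tool would score about 1 or less. The documents do not support this:

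- Both ranges are assumptions.
- The ratio is over all skin patients, whereas the ratings are by disease.
- The same inputs imply between 10 × 5 × 17.33, about 870, and 30 × 10 × 17.33, about 5,200 skin patients. Against 100 recruited under an include-all rule, either few are eligible and consent, so coverage of those is high, or recruitment ends early and the weekly rate is wrong.
- No section presents item 1 as a measure of exposure to the tool.

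**Conclusion.** The point holds as a weakness in measurement. Items 3-7 are not tied to patients assessed with the tool, no item counts those patients, and the minimum of 50 per centre gives no exposure per physician or disease. The ratings that carry the main variable therefore cannot separate benefit when the tool is used from how often it was used.

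The size is unknown. The documents fix only the overall rate, about 5.8 tool patients per week in both centres together. Anything per physician depends on an unstated number of physicians, and coverage within a rated disease cannot be derived. It would go too far to say that the main variable mostly reflects the share of patients enrolled. That would require respondents to adopt the practice-wide reading and coverage to be low, and the documents show neither. The change is worth making before the first form is completed, because exposure not recorded then would have to be recalled later.

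**What to change.** Amend Annex I as follows:

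1. Open items 3-7 with: *In the patients you assessed with Legit.Health since the study began.*
2. For each disease, ask how many patients the respondent assessed with the tool up to the form date, and offer *not used / no case* as an answer.
3. Report every disease rating with its count, and keep *not used* out of the averages. Counts by physician and disease will often be small, so show them beside the ratings and do not stratify by them.
4. Keep item 1 as a description of caseload only.
5. Give dermatologists wording that fits their role. Procedures to be performed by the specialist physician describes standard routine and no use of the tool, so the opening above could leave them nothing to rate. The plan should say what their ratings refer to.

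The count can be stated by the physician on the form, at the price of some recall error. Taking it from the platform would be more exact, but needs two things: reconciliation with the statement in Patient identification that patient data will not be analysed, and a link from each case to the physician's study code, which the documents do not describe. Patient identification needs reconciling in any case with Variables, which lists patient-level data to be collected.

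The cost is a small change of wording, made by written amendment with ethics committee review as sections 6 and 8 provide, and one extra number per disease on each form. The downside is that the experience behind each rating will look smaller than the caseload figure suggests.

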## Hypothesis

The hypothesis guiding this study is that the Legit.Health platform, developed by AI LABS GROUP SL, significantly increases the appropriateness of referrals to dermatology.

This hypothesis is based on the notion that artificial intelligence introduces several significant changes to the diagnostic process:

- Greater sensitivity and specificity than a primary care physician in diagnosing skin conditions, especially in differentiating between malignant and benign lesions.
- It provides the security of a clinically validated second medical opinion.

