#### Inclusion criteria:

- Patients with suspected of having the following pathologies in Primary Care:
  - Tumor pathology
    - Benign
      - Histiocytoma
      - Seborrheic keratosis
      - Angiomas
    - Precancerous
      - Actinic Keratosis
    - Suspected malignancy:
      - Basal cell carcinoma
      - Squamous cell carcinoma
    - Pigmented lesions
      - Melanocytic nevus
      - Malignant melanoma
  - Inflammatory pathology
    - Psoriasis
    - Atopic dermatitis
    - Urticaria

- Hidradenitis suppurativa
- Lichen planus
- Infectious pathology
  - Viral warts
  - Molluscs
  - Herpes simplex
- Patients aged 18 years or older.
- Patients who have signed the informed consent for the study.

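### Annex I items 3 to 7 cannot record harm, cannot separate 'not seen' from 'no effect', and collect 11 of the 16 study conditions only where the tool had an impact

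*Combined protocol and SAP*

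**What the plan says.** Under Variables (section 4), the main variable is the platform's clinical utility, and "clinicians will complete the Clinical Utility and Satisfaction Questionnaire (Annex I") to measure it. Section 5 has primary care physicians and dermatologists complete the form at 2 and 4 months.

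Items 3 to 7 of Annex I ask for impact from 0 to 10. Item 3 is typical: "where 0 is “no impact” and 10 is “great impact”) on the accuracy of your diagnostic decisions for each of the following diseases". Item 4 asks about impact "in relation to reducing the time to issue your diagnostic decision for each of the following diseases". Items 5 and 6 cover therapeutic decisions and monitoring. Item 7 asks about impact "on the efficiency of interconsultations/referrals to the dermatology service (in cases where referral applies) for each of the following diseases".

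Each item pre-prints the same five diseases: urticaria, psoriasis, hidradenitis suppurativa, melanoma and atopic dermatitis. The sixth line is for other diseases, and in item 3 it reads "Other (add any other diseases where the tool has had an impact at this point and rate the impact from 0 to 10". The matching lines in items 4 to 7 carry the same condition but do not repeat the request for a rating.

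The Inclusion criteria name 16 conditions, among them "Basal cell carcinoma". The rationale under Hypothesis expects better diagnosis, "especially in differentiating between malignant and benign lesions".

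The documents give no scoring rule, no composite, and no rule for blank answers.

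**The concern.** Three features of items 3 to 7 limit what the main variable can show.

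- **No negative side.** A physician whom the tool misled, or whose referral became less efficient, has no place on the scale to say so. Item 4 asks only about time saved, so a slower decision cannot be scored.
- **No not-seen answer.** For a disease in which the physician never used the tool, the form offers only a number or a blank. A 0 or a guess cannot be told apart from a rating by someone who used the tool and found no effect.
- **Selection on success.** Unlisted conditions are invited only where the tool had an impact. A condition in which it was used without effect is left out and is not counted as 0.

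At stake is the reading of the disease-level scores. For listed diseases a low score has no clear meaning. For unlisted conditions the scores are inflated. Because no scoring rule exists, nothing later in the plan corrects this, and data already collected on the form cannot be repaired.

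**Working it through.** The plan states no figure on this point, so there is none to reproduce. The check is a count, followed by illustrations under stated assumptions.

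**Coverage (Inclusion criteria against Annex I).**

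| Group | Named | Pre-printed | Only through 'Other' |
|---|---|---|---|
| Tumour | 8 | 1 (melanoma) | 7 |
| Inflammatory | 5 | 4 | 1 (lichen planus) |
| Infectious | 3 | 0 | 3 |
| Total | 16 | 5 | 11 |

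The seven unlisted tumour conditions are histiocytoma, seborrheic keratosis, angioma, actinic keratosis, basal cell carcinoma, squamous cell carcinoma and melanocytic nevus. The contrast between malignant and benign lesions is therefore rated systematically only for melanoma.

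**Selection through 'Other' (assumed values).** Let the true impact be 8 in 3 of the 11 unlisted conditions and 0 in the other 8.
- Followed as worded, the form collects three scores of 8, with a mean of 8.0.
- Asking about all 11 gives (3 × 8 + 8 × 0) / 11 = 2.2.

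**Floor at zero (assumed distribution).** Let the perceived net effect be normal with mean 0, and let every negative experience be entered as 0. The mean recorded score is SD / √(2π).
- SD 2: 0.80
- SD 3: 1.20
- SD 4: 1.60

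The true mean is 0 in each case.

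**Chance of having no case (assumed shares).** Expected sample size sets at least 50 patients per centre, with no minimum per disease or per physician, and the number of physicians is not given. For a disease with share p and a physician with n patients, P(no case) = (1 − p)^n.

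| Patients per physician (physicians if N = 100) | p = 1/16 | p = 0.02 |
|---|---|---|
| 5 (20) | 72% | 90% |
| 10 (10) | 52% | 82% |
| 25 (4) | 20% | 60% |

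At n = 10 and p = 1/16, about 5 × 0.524 = 2.6 of the five listed diseases would have no case behind the rating. Item 1 asks only for total skin patients per week, so exposure per disease cannot be recovered from the form.

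**Direction for unseen diseases.** If seen diseases are rated 8 and unseen ones are entered as 0, the mean of the five is:
- 1 unseen: 8 × 4/5 = 6.4
- 2 unseen: 8 × 3/5 = 4.8
- 3 unseen: 8 × 2/5 = 3.2

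This works against the tool, whereas guesses could go either way.

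**The case against.** A reader might infer that Annex I as a whole can only favour the tool. The text does not support that. Item 8 runs from not at all to very satisfied, and the patient-satisfaction rating has the same anchors. Two recommendation questions can be answered no, and the last open field asks for features that add nothing. Within items 3 to 7, a 0 is a null result and not a favourable one. This stands, and it confines the point to items 3 to 7. It does not repair them: item 8 measures satisfaction, and no other numeric item addresses the five aspects of utility.

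A reader might also infer that physicians must rate diseases they have not seen. No text makes a rating mandatory or forbids a blank, and item 7 is limited to cases where referral applies. What the documents show is that no not-seen answer is offered.

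The sponsor could add that the hypothesis concerns appropriateness of referral, with discrimination of malignant from benign lesions only as supporting rationale. Referral appropriateness and both diagnoses are recorded by the specialist (section 5), and diagnostic correlation is a secondary variable. A misdiagnosis thus has a place outside the annex. That is correct, but those records do not enter the main variable.

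Finally, this is a proof-of-concept pilot of perceived utility with no test or success threshold. That lowers the severity. It does not make the scores easier to interpret.

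**Conclusion.** The point holds for items 3 to 7 and should be fixed. These items cannot record a harmful effect as harm and give a 0 two possible meanings. They collect 11 of the 16 inclusion conditions only when the tool had an impact. The count is exact and rests on the documents alone. The upward skew for unlisted conditions follows from the wording of 'Other'. For the not-seen problem the direction is unknown.

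The documents do not support a claim that the primary result is biased by a known amount, because they define no summary score. The word impact carries no sign in items 3 and 5 to 7, so how a respondent would code harm is itself uncertain. The +0.8 to +1.6, the 8.0 against 2.2, and the no-case percentages are illustrations. They depend on an assumed distribution, assumed true impacts, assumed disease shares and an unstated number of physicians.

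**What to change.** Amend Annex I before the 2-month questionnaire:

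1. Reword 'Other' to 'any other condition in which you used the tool, whether or not it helped', with a rating for each in every one of items 3 to 7.
2. Add a 'not seen with the tool' box for each disease and leave those cells out of the denominator.
3. Use a two-sided scale in items 3 to 7 (worse, no change, better), and word item 4 as effect on the time.
4. Optionally, add rows for the unlisted groups (benign, precancerous, suspected malignancy, other pigmented, lichen planus, infectious) and keep melanoma as its own row.

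The cost is one amendment and scores not comparable with the 0-10 version. With the six group rows the form grows to (5 + 6) × 5 = 55 ratings, against 5 × 5 = 25 now. Pre-printing all 16 conditions would need 16 × 5 = 80, which is a heavier burden and not necessary. Mean scores could move either way: a negative side lowers them, while removing zeros for unseen diseases raises them. These changes do not supply a summary score, which the plan still has to define.
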